No formal statistical analyses will be done comparing primary or secondary efficacy endpoints between the Waiting Period on commercial product and the IMP Treatment Period. However, any efficacy endpoints measured during both the Waiting Period on commercial product and IMP Treatment Period may be summarized side-by-side using the appropriate descriptive statistics. For the Waiting Period on commercial product, the summary descriptive statistics will be aggregated over all commercially licensed products.

Safety Endpoints

Evaluation of safety includes the analysis of laboratory investigations and the analysis of adverse events.

Laboratory Data:

A summary by treatment period (Waiting period, IMP treatment period) will be produced for each of the laboratory parameters at each visit. These safety summaries will include descriptive summary tables and the data will be summarized in the form of frequency count, mean, standard deviation, median, minimum and maximum by treatment period and visit.

Adverse Events:

The seriousness, severity and relationship to the study drug of adverse events (AEs) will be observed and recorded on repeated administrations of the study drug using the MedDRA dictionary for the coding of AEs and serious adverse events (SAEs).

The number and proportion of subjects who have one or more AEs will be tabulated by seriousness, severity, and relationship to treatment according to body system and treatment period. Temporally associated AEs will be similarly summarized. Rates of AEs will be estimated on a per infusion per subject basis and tabulated by seriousness, severity, and relationship to treatment according to body system and treatment period.

The observed proportion will be reported for infusions with one or more temporally associated (during and within 72 hours after the end of the infusion) AEs (including any AEs considered product related). Infusional AEs will also be tabulated by the prevailing infusion rate.

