10.2.2 Subject Monitoring

The recommended infusion rates mandated by the protocol must be closely followed. Subjects must be closely monitored and carefully observed for any symptoms throughout the infusion period as per the protocol requirements.

Certain severe ADRs may be related to the rate of infusion.

Certain adverse reactions may occur more frequently:

- in patients with hypo- or agammaglobulinemia with or without IgA deficiency
- in case of high rate of infusion

All subjects will be monitored for the first hour after each infusion, except for the first infusion where they will be monitored for 3-4 hours after the infusion. During this time, the subject will be observed in order to detect potential adverse signs and conduct the post-infusion 60-minute vital sign measurement and assessment for signs of hemolysis or thrombosis. Handling of Infusional and Temporally Associated AEs

Infusional and temporally associated AEs will be closely monitored. For AEs that occur during infusions, the infusion rate in effect at the time of onset of the AE will be captured.

IMP will be administered according to the infusion rate titration schedule in Section 13.6.

Note: The dose and administration of CP for subjects on the Waiting Period will be per standard care, as determined by the Investigator in consultation with the treating physician.

If an infusional AE occurs during the first treatment course, the study staff will initiate one of the following actions, which will be graded from 1 to 4 depending on the nature and/or severity of the event:

1. Reduce the current infusion rate to one-half the rate of the infusion at which the AE was observed; or
2. Reduce the rate of the infusion more than one-half the rate at which the AE was observed, as necessary to subside symptoms; or
3. Reduce the rate of the infusion to one-half, or progressively reduces more than one-half, the rate at which the AE was observed and then stops the infusion, as necessary to subside symptoms; or
4. Stop the infusion to subside symptoms.

The study staff will evaluate the subject's AE and then:

- increase or resume the infusion at a rate tolerated by the subject once the symptoms have subsided; or

- stop the infusion and not resume it.

If a subject has an infusional AE at the same infusion rate twice, then subsequent infusion rate escalation, if any, should be halted at the rate before the AE, depending on the severity of the AE.

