13.6.2.2 IMP Infusion Rate for Infusion 3 Onward

The rate for Infusion 3 onward will follow the same algorithm of infusion rate increase for the first two doses, but the increases can be implemented every 15 minutes instead of 30 minutes.

If an AE occurs, the infusion rate must be decreased to the rate of the previous step; in addition, the infusion should be stopped if deemed appropriate by the Investigator.

14 Records Management

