9. EVALUATION OF TREATMENT EXPOSURE AND COMPLIANCE

9.1. Exposure to Study Treatment

Subject exposure to the study drug (IMP or CP), displayed as total number of infusions received, number of infusions per subject, total average IGIV dose per infusion (mg/kg) received, total weeks on study drug, lot numbers of IMP, number of subjects completing ≥ 6 and 12 months of dosing, and total exposure time in years will be summarized and listed.

CP administered will be summarized by the following IGIV products:

- Gammaplex 5%
- Carimune 6%
- Gammagard Liquid 10%
- Gamunex-C 10%
- Octagam 10%
- Privigen 10%
- Octagam 5%
- Bivigam 10%
- Flebogamma 10%

Study drug administration data, including start and stop times and infusion rates, and treatment infusion interruption data for CP and IMP will also be provided in a listing.

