11.1. Temporally Associated TEAEs (TAAEs)

The FDA recommends that for a novel IGIV formulation, a study should demonstrate a TA rate of not more than 40 TAAEs associated with the study drug per 100 administrations. A TAAE should be established as related to the infusion of study drug by implicating temporal association.

For the purpose of this study, TAAEs are considered temporally associated with the study drug infusion if they occur in the period from the start of the infusion until 72 hours after the end of the infusion. The overall TAAE rate considered temporally associated with the study drug infusion and the rate of at least possibly related TAAEs considered temporally associated with the study drug infusion will be considered. A one-sided 95% upper confidence boundary for this percentage will be calculated by using the normal approximation.

The proportion of infusions with a TAAE will be analyzed using a non-inferiority test, with the objective of demonstrating that the percentage of infusions with one or more infusional TAAE is less than 40%. This will be achieved by calculating the percentage of affected infusions for each subject, and then calculating a (weighted) mean of these percentages, with a 95% (one-sided) confidence interval. A suitable transformation will be used if appropriate. The upper limit of this confidence interval should be below 40% in order to demonstrate non-inferiority. Weighting will be based on the number of IMP infusions for which data are available. This method of calculation of the confidence interval takes proper account of the observed intra-subject correlation because it is based on a single summary data point for each subject.

The following SAS code can be used in the analysis.

```
proc genmod data=xxxxxx descending ;  
  class x1 x2 ...label/ ;  
  model resp_dur = / cl dist = bin link = logit alpha=0.1 ;  
  repeated subject = xxx / type=exch ;  
run;
```

TAAE will be summarized by:

- during the infusion (i.e., infusional TEAEs)
- within 1 hour of infusion
- within 4 hours of infusion
- within 24 hours of infusion
- within 72 hours of infusion

A summary of descriptive statistics will be provided for the IMP subjects in the safety population.

The following observations will be summarized using the standard set of summary statistics.

- Summary of TAAEs by infusion rate;
- Total number of TAAEs and infusional TEAEs;

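### The SAP's table of temporally associated AEs by infusion rate covers events that have no infusion rate and has no time-at-rate denominator, so at most doses it may show an excess at the top rate without any rate effect

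*SAP*

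**What the plan says.** SAP 11.1 counts an AE as temporally associated "if they occur in the period from the start of the infusion until 72 hours after the end of the infusion". It then introduces a list of outputs with "The following observations will be summarized using the standard set of summary statistics", and the first item is "Summary of TAAEs by infusion rate". The items that follow name TAAEs and infusional TEAEs together; the by-rate item names TAAEs alone. Nothing in the section says how an event after the infusion gets a rate, or what the denominator at each rate is.

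The protocol is narrower. Section 10.2.2 states: "For AEs that occur during infusions, the infusion rate in effect at the time of onset of the AE will be captured". The synopsis, under the statistical methods for adverse events, states: "Infusional AEs will also be tabulated by the prevailing infusion rate".

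Protocol 13.6.2.1 sets the escalation for Infusions 1 and 2: 0.01, 0.02 and 0.04 mL/kg/min for 30 minutes each, then the remainder at a maximum of 0.06-0.08 mL/kg/min depending on body weight, each increase permitted if the previous rate was tolerated. From Infusion 3, under Protocol 13.6.2.2, "the increases can be implemented every 15 minutes instead of 30 minutes".

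SAP 9.1 lists "Study drug administration data, including start and stop times and infusion rates, and treatment infusion interruption data" for each product, and SAP 11 collects the date and time of AE onset.

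**The concern.** Examining rate-related AEs is a stated safety objective in Protocol 2.3.4 and SAP 2.3, and this is the item in SAP 11.1 that breaks AEs down by rate.

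There are two problems. First, the event set includes events for which no rate is in effect. They must be left out, put in a separate row, or given a rate by some rule, and the choice can change the table greatly. Second, even for events during the infusion, the time spent at each rate is set by the escalation schedule and the dose. Without time at rate, a rate under which subjects spend longer collects more events. A reader looking for a rate effect could not tell it from exposure time.

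**Working it through.** The documents state no expected figure for this table, so there is none to reproduce. The check is how infusion time divides over the rates.

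**Inputs.** Dose 200-800 mg/kg (Protocol 4.3.1 and 13.6.1). Concentration 100 mg/mL (Protocol synopsis), so volume = dose/100 mL/kg. Rates and step lengths from Protocol 13.6.2. Infusions per subject: 13 on the 28-day cycle and 17 on the 21-day cycle (Protocol Table 4).

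**Assumptions.** Every step is tolerated, there are no interruptions, the 8.0 mL/min cap does not bind (at 0.08 mL/kg/min it binds above 8.0/0.08 = 100 kg), and the AE hazard per minute is constant and unrelated to rate.

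**Volume given in the three lower steps.**
- Infusions 1-2: 30 × (0.01 + 0.02 + 0.04) = 2.10 mL/kg in 90 minutes.
- Infusion 3 onward: 15 × 0.07 = 1.05 mL/kg in 45 minutes.

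**Minutes at the top rate** = (dose/100 − volume in lower steps) / top rate. At 500 mg/kg and 0.08 mL/kg/min:
- Infusions 1-2: (5 − 2.10)/0.08 = 36.3 of 126.3 minutes, 28.7%.
- Infusion 3 onward: (5 − 1.05)/0.08 = 49.4 of 94.4 minutes, 52.3%. Against one lower step, 49.4/15 = 3.3.

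The full-course share weights two infusions at 30-minute steps and the remaining 11 or 15 at 15-minute steps. For example, at 300 mg/kg, 0.08 and 13 infusions: (2 × 11.25 + 11 × 24.375)/(2 × 101.25 + 11 × 69.375) = 290.6/965.6 = 30.1%.

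Share of infusion time at the top rate. The first three ranges run from a 0.08 to a 0.06 top rate, the full-course range also over 13 and 17 infusions. The last column is top-rate minutes over one 15-minute step at a 0.08 top rate.

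| Dose (mg/kg) | Infusions 1-2 | Infusion 3 onward | Full course | Ratio, Infusion 3 onward |
|---|---|---|---|---|
| 200 | 0% | 20.9-26.0% | 16.3-21.8% | 11.9/15 = 0.8 |
| 300 | 11.1-14.3% | 35.1-41.9% | 30.1-37.7% | 24.4/15 = 1.6 |
| 400 | 20.9-26.0% | 45.0-52.2% | 40.2-48.4% | 36.9/15 = 2.5 |
| 500 | 28.7-34.9% | 52.3-59.4% | 47.7-55.9% | 49.4/15 = 3.3 |
| 600 | 35.1-41.9% | 57.9-64.7% | 53.5-61.5% | 61.9/15 = 4.1 |
| 800 | 45.0-52.2% | 65.9-72.0% | 62.0-69.3% | 86.9/15 = 5.8 |

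Under the constant hazard these shares are also the expected shares of infusional AEs at the top rate. An even split over four rates is 25%. Over the full course the top rate exceeds this at 300 mg/kg and above, but not at 200 mg/kg. In Infusions 1-2 at 200 mg/kg the top rate is never reached, because the dose is 2.0 mL/kg and the lower steps can deliver 2.10. The top rate gets more time than one lower step only above 390 mg/kg (top rate 0.06) or 450 mg/kg (0.08) in Infusions 1-2, and above 195 or 225 mg/kg from Infusion 3.

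**Post-infusion events.** The 72 hours after the infusion are 4320 minutes. From Infusion 3 that is 4320/(4320 + infusion minutes) = 96.4% to 98.7% of the TAAE window, a stretch with no rate in effect. If such events were given the last rate, which is an assumption and not an SAP rule, the top rate at 500 mg/kg and 0.08 would take (4320 + 49.4)/(4320 + 94.4) = 99.0% of TAAEs under the constant hazard.

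**The case against.** A reader might infer that the table is certain to show an excess at the top rate. The documents do not support that. The SAP states no rule for post-infusion events: a not-applicable row, or classifying infusions by their maximum rate with infusions as denominator, would not produce the pile-up. Escalation is permissive, and Protocol 10.2.2 allows reduced rates and halted escalation after an AE, so some infusions will never reach the top rate. The top step is itself a weight-dependent range and may be split into more than one category. At low doses the direction reverses: at 400 mg/kg and 0.08 in Infusions 1-2, the top rate gets (4 − 2.10)/0.08 = 23.75 minutes against 30 for a lower step. All of this stands, and it makes the excess conditional.

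A reader might also infer that the SAP withdraws the protocol's table, or that its own table gives counts only. Neither follows. SAP 1 says the SAP supplements the protocol, Protocol 12.3.4 still lists rate-related AEs, and SAP 6.1 includes percentages for categorical data. Protocol 12.3.1 adds rates per subject per infusion for counts. But none of these is a time-at-rate denominator, and none assigns a rate to a post-infusion event.

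Finally, the time-at-rate problem applies equally to the protocol's infusional table, and a per-hour rate would not isolate a rate effect. Both are true. They argue for adding the denominator and reading it cautiously, not for leaving it out.

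**Conclusion.** The point holds in a limited form. As written, SAP 11.1 tabulates by infusion rate a set of events most of whose time window lies after the infusion, although a rate at onset is captured only during it. It gives neither an attribution rule nor a time-at-rate denominator. The table may show, and at most doses in the permitted range would be expected to show, an excess at the top rate with no rate effect. The size depends on dose and infusion number, as tabulated above, and rests on full escalation without interruption and a constant hazard. At 200 mg/kg no excess is expected over the full course. Only under the assumed last-rate attribution would nearly all TAAEs fall at the top rate.

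The consequence is for interpretation of a stated safety objective. The table carries no test, and neither the criterion of fewer than 40 affected infusions per 100 nor the primary endpoint depends on it. The change is worth making before the tables are programmed.

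**What to change.** In SAP 11.1:

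- Restrict the by-rate table to infusional TEAEs, classified by the rate in effect at onset, as in the protocol.
- At each rate, report events per infusion-hour and the number of infusions reaching that rate, separately for Infusions 1-2 and Infusion 3 onward.
- State that post-infusion TAAEs carry no rate and stay in the existing 1, 4, 24 and 72 hour summaries.

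The cost is SAP wording and one derivation, minutes at each rate. It depends on the time of each rate change being recorded. SAP 9.1 lists start and stop times and rates, and Protocol 6.3 schedules vital signs after each rate increase, but neither states that every change is timed. If they are not timed, use the number of infusions reaching each rate as the denominator.

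The table stays descriptive. Within an infusion, rate rises with elapsed time and cumulative dose, and higher rates are reached mainly by those who tolerated the earlier steps. A footnote should say so.

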11.2. Treatment-Emergent Adverse Events

An overall summary table of TEAEs, including subjects experiencing at least one TEAE, at least one TEAE related to study drug, at least one TAAE, at least one infusional TEAE, at least one adverse reaction, at least one TEAE leading to study discontinuation, and at least one TEAE leading to death will be presented.

TEAEs including TAAEs, infusional TEAEs, and adverse reactions will be summarized by SOC and PT, showing the number and percentage of subjects experiencing a given event. In addition, TEAEs and TAAEs will be summarized by SOC, PT and worst severity; TEAEs will also be summarized by SOC, PT and relationship to study drug.

TESAEs will be similarly summarized. The number and proportion of subjects who have one or more TESAEs, and who have one or more serious TAAEs, will be presented. TEAEs will also be tabulated for the minimum of 30 subjects who received the highest average dose of IMP.

A subject will be counted only once for each preferred term when multiple AEs are coded to the same preferred term. If a subject experiences multiple AEs coded to the same preferred term, the maximum toxicity grade will be used for the summary.

11.3. Death

Subjects whose AE outcome is death will be listed.

11.4. Study Discontinuation due to a TEAE

Incidence of TEAEs and related TEAEs leading to study discontinuation will be summarized by SOC and PT. Additionally, subjects who discontinued from the study due to TEAEs will be listed. Subject discontinuation will be determined from the evaluation (where reason for termination is AE) and the specific AE will be determined from the AE CRF page (where action taken is discontinuation of study drug).

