8.1.1 Immunogenic Reactions

Diagnosis of an immunogenic reaction that may lead to a thrombotic event will be based on treatment-emergent positive anti- β 2GPI and β 2GPI-DI antibody titers, defined as an antibody titer of ≥ 40 U found twice on tests that are at least 12 weeks apart and/or on treatment-emergent positive anti- β 2GPI and β 2GPI-DI antibody titers > 20 U but < 40 U in combination with a treatment-emergent thrombotic or thromboembolic event (Unlu et al., 2015) by these definitions will be considered significant events. If any subject after receiving IMP seroconverts from negative to positive, with an elevated rising antibody titer at least 12 weeks apart, then all prior retention samples for β 2GPI and/or β 2GPI-DI for all subjects should be analyzed.

Subjects who develop treatment-emergent anti- β 2GPI and/or β 2GPI-DI antibody titers > 20 U following exposure to IMP will be followed closely by the investigator for thrombotic and/or thromboembolic events. These subjects will have periodic (no more than 8 weeks apart) anti- β 2GPI and β 2GPI-DI antibody titer testing until they have completed 52 weeks of treatment with IMP or until immunogenicity titers have stabilized or are declining over 3 consecutive treatment cycles (21 or 28 day cycles), whichever is later.

As shown in Figure 2:

1. Any subject who has a significant event as defined above for anti- β 2GPI and/or β 2GPI-DI antibodies while being treated with IMP will permanently discontinue treatment with the IMP. The subject will remain in the study for safety assessments up to the time of the final follow-up phone call after LTSF (see Section 7.11).
2. The occurrence of two such significant events as defined above for anti- β 2GPI and/or β 2GPI-DI antibodies will be referred to the DSMB for an urgent ad-hoc review to determine if this qualifies as a potential study-stopping event as defined above.

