8.1.3 Hemolysis

As shown in Figure 2:

- Investigator will examine subjects for clinical signs of hemolysis (Section 6.12.2). Positive assessments will lead to a full work-up for hemolysis, as appropriate, according to the facility's standard of care.
- For all subjects, a drop of ≥ 2.0 g/dL from the pre-infusion hemoglobin level or clinical signs of hemolysis between visits will lead to a full hemolysis work-up (Section 6.9).
- Any subject who is diagnosed for a hemolysis event based on clinical and laboratory assessment while being treated with IMP will permanently discontinue treatment with the IMP and will receive standard medical care. The subject will remain in the study for safety assessments up to the time of the final follow-up phone call after LTSF (see Section 7.11). Any such event will be referred to the DSMB for an urgent ad-hoc review to determine if this event qualifies as a potential study-stopping event as defined above.
- Any subject who is diagnosed with hemolysis based on clinical and laboratory assessment while being treated with the commercial product will receive standard medical care and continuation in the study will be at the discretion of the Investigator. If the subject is terminated from the study, the PI will determine continued treatment for managing the disease, in consultation with the subject's treating physician and per standards of care. The subject will remain in the study for safety assessments up to the time of the final follow-up phone call after LTSF (see Section 7.11).
- If two or more subjects experience confirmed hemolysis events in the trial as a whole in subjects receiving IMP, the DSMB will put the study on temporary hold while an assessment is made. All treatments with the IMP will be discontinued until the investigator, the DSMB, and the FDA have reviewed safety data for subjects enrolled. During this time, no new subjects will be enrolled. If a subject should require a scheduled infusion during this time, they will continue therapy with a commercially available preparation (CP). IMP infusions will be recommenced if approval to continue the study is given by the DSMB and FDA.

The IRB/IEC and the US FDA/appropriate regulatory authority for trials outside the US will be immediately notified of any suspected ADRs involving hemolysis.

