7. SUBJECT ENROLLMENT AND DISPOSITION

7.1. Subject Disposition

Subject disposition information will be summarized for all subjects by cohort and by Treatment Period. Summaries will include: the number of enrolled subjects, the number of subjects in each analysis population, the number of subjects completing the study, the number of subjects who are ongoing (for interim analyses only), the number of subjects discontinuing the study and the primary reason for study discontinuation. Additionally, total number of enrolled subjects by site will be summarized and listed.

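### SAP 7.1, 11.2 and 11.4 count discontinuation only at study level, so subjects whom the protocol takes off IMP but keeps in follow-up can be left out of the discontinuation and disposition tables

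*SAP*

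**What the plan says.** **SAP.** The disposition summary in section 7.1 includes "the number of subjects discontinuing the study and the primary reason for study discontinuation". It has no line for completing or stopping IMP treatment. The overall TEAE table in section 11.2 has a row for subjects with "at least one TEAE leading to study discontinuation" and none for stopping study drug. Section 11.4 plans a table, "Incidence of TEAEs and related TEAEs leading to study discontinuation will be summarized by SOC and PT", and a listing, "subjects who discontinued from the study due to TEAEs will be listed". Its case-finding rule has two parts joined by an and. The subject is identified first: "Subject discontinuation will be determined from the evaluation (where reason for termination is AE". The event is then named: "the specific AE will be determined from the AE CRF page (where action taken is discontinuation of study drug".

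**Protocol.** Stopping IMP and leaving the study are different things. Under 8.1.3, a subject diagnosed with hemolysis on IMP "will permanently discontinue treatment with the IMP and will receive standard medical care". Section 8.1.2 has the same rule for thromboembolic events, and 8.1.1 requires a permanent IMP stop for a significant anti-β2GPI or β2GPI-DI antibody event. In all three, the subject stays on for follow-up; in the words of 8.1.1, "The subject will remain in the study for safety assessments up to the time of the final follow-up phone call" after the LTSF. Section 7.11 describes those visits, and section 16.2 separately lets a subject give up treatment alone and be followed for safety.

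**The concern.** In a single-arm safety study, the number of subjects who permanently stopped the product because of an adverse event is a basic tolerability result. The protocol names three kinds of event that force such a stop, and for each it keeps the subject in the study. The SAP's discontinuation outputs are all defined by leaving the study. A programmer who follows the text could therefore report no AE discontinuation for a subject taken off IMP for hemolysis, thromboembolism or antibodies. The SAP knows that such subjects can exist: footnote bb to its schedule in section 14.2 continues their follow-up. It gives them no place in a discontinuation table.

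**Working it through.** The SAP states no figure to reproduce. The check follows one case through the rules and then adds simple proportions.

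**Step 1: a hemolysis case on IMP that completes follow-up.**
- Protocol 8.1.3: IMP is stopped permanently and the subject remains in the study until the final call.
- SAP 7.1: the subject has not discontinued the study, so is not in the count or the reasons.
- SAP 11.4, first part: entry needs a termination record with AE as the reason. A subject who completed the follow-up need not have one.
- SAP 11.4, second part: the AE page may show study drug discontinued, but this field names the event for someone already identified. It is not a second way in.
- SAP 11.2: the row is for study discontinuation, so the subject is not in it.

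The same path applies to thromboembolic events (8.1.2) and significant antibody events (8.1.1).

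**Step 2: is the stop counted elsewhere?** SAP 9.1 reports infusions per subject and the numbers completing at least 6 and 12 months of dosing. A shortfall in dosing would show there, but without its reason. No SAP section plans a table or listing of TEAEs leading to permanent discontinuation of IMP.

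**Step 3: the undefined form.** SAP 11.4 does not say which record the evaluation is. The eCRF is not among the documents.
- If it is an end-of-study record, and subjects who finish follow-up are not entered as terminated for AE, they are omitted.
- If it is the form for the treatment completion/termination visit (Protocol 7.9, which does speak of treatment being terminated), or if sites enter AE as the reason after follow-up ends, they are included. They are then labelled as having left the study, which the protocol says they did not.

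On the first reading the subjects are missing; on the second they are mislabelled. Neither gives a clean count of IMP stops.

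**Step 4: CP against IMP.** For thrombosis and hemolysis on CP, 8.1.2 and 8.1.3 leave continuation to the Investigator. If the subject is terminated, the same bullets still keep the subject under safety assessment until the call after LTSF. So if staying through LTSF means no study termination, terminated CP cases are missed as well. If termination and LTSF can coexist, IMP cases can be counted as well. Neither reading gives a direction.

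**Step 5: size per missed subject.** Planned enrollment (SAP 3) is about 75, with about 50 in Cohort 1 and 25 in Cohort 2.
- Overall: 1/75 = 1.3%
- Cohort 1: 1/50 = 2.0%
- Cohort 2: 1/25 = 4.0%
- Illustration with an assumed two such subjects, both omitted: 2/75 = 2.7% stopped IMP, against 0% shown from these causes.

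**The case against.** The best defense is that nothing is lost. The events themselves are reported: TEAEs by system organ class, preferred term, severity and relatedness (SAP 11.2), and hemolysis, clinical signs of thrombosis and antibody data in SAP 11.5.1 to 11.5.4. Protocol 8.1.2 and 8.1.3 send each thromboembolic or hemolysis case on IMP to urgent DSMB review. The author of SAP 11.4 may also have meant one event, since the rule pairs termination with stopping study drug. The protocol itself speaks of treatment termination, and it describes CP subjects who are terminated yet remain under assessment.

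Much of this stands, and it rules out three stronger readings that a reader might infer.
- That every protocol-mandated IMP stop is missed. This is not established, because the form is undefined and may capture them.
- That the gap favors IMP in the side-by-side display. The documents do not support this, because the CP bullets in 8.1.2 and 8.1.3 carry the same retention in follow-up.
- That the three event types vanish from the safety report. They do not. One qualification applies: an antibody titer finding reaches the TEAE tables only if it is recorded as an AE, which the documents do not explicitly require.

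What the defense does not supply is any output giving the number of subjects who permanently stopped IMP because of a TEAE. A rule that two programmers could carry out with different counts also still needs settling.

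**Conclusion.** The point holds as a gap in definition. The SAP's discontinuation and disposition outputs are at study level, while the protocol's three mandatory stops are at treatment level with the subject retained. On the literal wording these subjects can be left out of SAP 7.1, 11.2 and 11.4; whether they would be rests on the unseen eCRF. The loss is confined to those outputs. The size per case is 1.3 points overall (2.0 in Cohort 1, 4.0 in Cohort 2), assuming enrollment as planned. The documents give no expected number of cases, so no total effect can be stated. The primary efficacy analysis is not affected.

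**What to change.** - **SAP 11.2 and 11.4:** tabulate by SOC and PT, and list, TEAEs leading to permanent discontinuation of study drug. Identify them from the action-taken field on the AE page, whatever the subject's study-termination status. Keep study discontinuation due to a TEAE as a separate row.
- **SAP 7.1:** report IMP treatment completed or discontinued, with the reason, separately from study completed or discontinued. Include a reason for stops triggered by antibody titer that were not entered as an AE, since the AE page alone would miss them.
- **SAP 11.4:** state which eCRF form the evaluation is, and how a subject who stops IMP and completes LTSF is recorded on it.

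The cost is SAP wording, one extra row and one listing. SAP 11.4 already relies on the action-taken field, so it needs no new data collection. The reported discontinuation rate may look slightly less favorable. No clinical rule changes.
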